6.7 Multicentre Studies

Due to the limited number of patients included in this trial, site level summary statistics will not be produced. A summary of number of patients per country will be generated, and only if relevant additional descriptive statistics for primary and secondary endpoints by country may be produced if any treatment by country effects are suspected.

6.8 Examination of Subgroups

In general subgroup evaluations will be performed in this study based on the stratification levels, high and intermediate risk patients. Statistical analyses will be performed on the primary endpoint of OS and proportion of 18-months survival and for the secondary endpoint of PFS. Analysis will be done for the FAS population.

Also, analysis of subgroup of patients from the site in Gothenburg that performs embolisation the day before operation will be evaluated descriptively for all biopsy data and for corresponding patient characteristics and demographic characteristics.

A summary overview of all Adverse Events, and summary of number of patients by AE intensity and relationship with treatment will be produced split by ilixadencel batch subgroup (INT and CCK).

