7.2.1.6 SFU[6W], SFU[12W], SFU[24W], SFU[36W], SFU[48W], and SFU[60W]

These visits are applicable for all patients unless locally CT-verified PD occurs. In case of PD this visit should be considered the End-of-Study Visit.

If SFU[60W] is scheduled ≥ 76 weeks since Screening this visit should be considered the End-of-Study Visit, *Section 7.2.1.7*.

TIME WINDOWS:

SFU[6W]: 6 weeks (± 7 days) after Sun-Start Visit
SFU[12W]: 12 weeks (± 7 days) after Sun-Start Visit
SFU[24W]: 24 weeks (± 7 days) after Sun-Start Visit
SFU[36W]: 36 weeks (± 7 days) after Sun-Start Visit
SFU[48W]: 48 weeks (± 7 days) after Sun-Start Visit
SFU[60W]: 60 weeks (± 7 days) after Sun-Start Visit

NB: The CT/MRI scans do not have to be done the very same day as the corresponding study visits. However, each CT/MRI scan has to be done within the specified time window for the corresponding visit.

ACTIVITIES AND ASSESSMENTS:

The same activities and assessments will be done at these visits as was done on Sun-Start Visit except for auto- and alloimmunization, *Section 7.2.1.5*. In addition to dispense of sunitinib, the site personnel will collect unused and empty sunitinib packages (distributed at the previous visit) from the patient for drug accountability, *Section 9.1.4*.

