10.5.2 Adverse Events

AEs will be recorded during the study period from Screening Visit to the completion of the End-of-Study Visit.

SAEs will be recorded during the study period from Screening Visit to the completion of the End-of-Study Visit or up to 30 days after last dose of IMP administered in the study, whichever occurs later.

AEs will be coded using the Medical Dictionary for Regulatory Activities (MedDRA) version 17.1. The severity of AEs will be graded using the NCI CTCAE version 4.0 [2]. For further information of definitions and reporting of AEs and SAEs, see *Section 11* below.

Medical conditions or diseases present before Screening Visit are only considered AEs if they worsen after Screening Visit. Non-serious events occurring after signing the Informed Consent Form (ICF) but before any assessments made at the Screening Visit are recorded as Medical History in the eCRF.

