- Sunitinib Start Visit (Sun-Start), five (5) to eight (8) weeks after Nephrectomy
- Sunitinib Follow-up Visits (SFU[6W] and SFU[12W]), every 6 weeks for 12 weeks or until locally CT-verified PD whichever occurs first
- Sunitinib Follow-up Visits (SFU[24W], SFU[36W], SFU[48W], and SFU[60W]), every 12 weeks until End-of study or until locally CT-verified PD whichever occurs first
- End-of-Study Visit (End-of-Study)

The above described visits are applicable to all randomized subjects after and including protocol version 4.0. Subjects entering the trial corresponding to protocol versions prior to this, were included following a visit pattern that was different for high and intermediate risk patients. Following this design intermediate risk subjects would only start sunitinib treatment after confirmed PD.

At the two (2) Vaccination Visits, the patients are be administered Intuvax (10 x10⁶ DCs) intratumorally in the viable part of their primary tumor. Vaccine from the same batch (i.e. the same donor) is be used at both occasions. The patient stay at the clinic at least four (4) hours after vaccination. Nephrectomy is done at least 3 days after the second vaccination and maximum 63 days after Screening. Sunitinib treatment is initiated five (5) to eight (8) weeks after nephrectomy, administered dose is in accordance with the SmPC/USPI.

All patients are encouraged to contact the clinic in between study visits if they experience adverse events (AEs) or have any concerns. If follow-up of any symptoms is needed between the planned visits, the patient are scheduled for a visit as soon as possible and applicable assessments are performed.

A diagram of the study design is provided in Figure 1, and a flow chart what all assessments to be conducted per visit are provided in Tables 1 and 2.

Post-study survival data (either patient alive or date of death) will be collected.

[figure not shown]

Figure 1 Overall Study Design

Table 1 Study Flow Chart

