14.3.1 Displays of Adverse Events

- 14.3.1.1 Summary of Adverse Events
- 14.3.1.2 Summary of Adverse Events by ilixadencel batch subgroup
- 14.3.1.3 Adverse Events by System Organ Class and Preferred term
- 14.3.1.4 Adverse Events: Number of Patients by Intensity and Relationship by Treatment
- 14.3.1.5 Adverse Events: Number of Patients by Intensity and Relationship by Treatment by ilixadencel batch subgroup
- 14.3.1.6 Serious Adverse Events by System Organ Class and Preferred term
- 14.3.1.7 Related Adverse Events by System Organ Class and Preferred term
- 14.3.1.8 Adverse Events by CTCAE grade and System Organ Class and Preferred term
- 14.3.1.9 Adverse Events occurring 4 hours following the Intuvax vaccination
- 14.3.1.10 Adverse Events occurring between first assessment at Screening and first Intuvax dose
- 14.3.1.11 Adverse Events occurring between first assessment at Screening and Nephrectomy
- 14.2.1.12 Related Serious Adverse Events by System Organ Class and Preferred term

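### The adverse-event tables split by vaccine batch have no vaccine-related time window, and the 4-hour reaction table is not split by batch, so a batch difference may be substantially diluted

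*SAP*

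**What the plan says.** SAP 6.8 names two outputs to be split by batch. The first is "A summary overview of all Adverse Events"; the second is a "summary of number of patients by AE intensity and relationship with treatment will be produced split by ilixadencel batch subgroup (INT and CCK"). In SAP Appendix 1 they become Table 14.3.1.2, "Summary of Adverse Events by ilixadencel batch subgroup", and Table 14.3.1.5, "Adverse Events: Number of Patients by Intensity and Relationship by Treatment by ilixadencel batch subgroup". No other table in section 14.3.1 carries a batch split. Table 14.3.1.9, "Adverse Events occurring 4 hours following the Intuvax vaccination", does not.

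The documents do not define INT, CCK or ilixadencel. I read ilixadencel as Intuvax, the only product in the trial given by donor batch.

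On the collection period, Protocol 10.5.2 says: "AEs will be recorded during the study period from Screening Visit to the completion of the End-of-Study Visit". That visit falls 78 ± 2 weeks after Screening (Protocol 7.2.1.7), but progression brings it forward: "In case of PD this visit should be considered the End-of-Study Visit" (Protocol 7.2.1.6).

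On pre-injection events, Protocol 12.1.12 has them summarised separately as an addition to the main summaries. SAP 6.3.10 has them summarised separately without saying that it is an addition, and does not say whether they leave the batch tables. Treatment-emergent status is planned as a flag in the AE listing.

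**The concern.** A batch can affect a patient only from the first injection on, and it is given twice, 14 ± 3 days apart, before surgery. The batch tables nevertheless take in everything recorded up to End-of-Study: the nephrectomy, the sunitinib period, and symptoms of progression, which Protocol 11.2 requires to be reported as AEs. The display closest in time to the injection, the 4-hour table, is the one without a batch column.

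The sponsor chose to look at safety by batch. If most patients in both batch groups have some AE for other reasons, similar columns could be taken as evidence that the batches do not differ when the table had little ability to show it. A visible difference could equally come from surgery or sunitinib.

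**Working it through.** **No figure to reproduce.** The documents give no AE rate, batch size or power for this comparison, and the trial size is not based on a power calculation (Protocol 12.2). About 90 × 2/3 = 60 patients are expected in the Intuvax arm.

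**Length of the vaccine window** (Protocol 9.1.1 and Table 2)
- Shortest, first injection to nephrectomy: 11 days between injections + 3 days = 14 days.
- Longest: day 2 to day 63 = 61 days.
- Full follow-up: 78 × 7 = 546 days. Shares: 14/546 = 2.6% and 61/546 = 11.2%. Progression shortens follow-up, so 546 days applies to a patient who completes.

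**Patients with at least one AE.** Let v be the risk of an AE in the vaccine window and b the risk of any other counted AE, assumed independent of v and equal in both batches. Then

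P(any AE) = 1 − (1 − v)(1 − b), so the batch difference = (v₂ − v₁)(1 − b).

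The share lost equals b, whatever v₁ and v₂ are. For illustration, v₁ = 5/12 = 41.7% (fever reactions and rash in the phase I study, Protocol 5.1), v₂ = 75% (assumed), and 30 patients per batch (assumed even split of 60). The last column is approximate power at two-sided 0.05. No batch test is planned, so it shows only how visible the difference would be.

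| b | Batch 1 | Batch 2 | Difference (points) | Share lost | Power |
|---|---|---|---|---|---|
| 0 (window only) | 41.7% | 75.0% | 33.3 | 0% | 0.76 |
| 0.5 | 70.8% | 87.5% | 16.7 | 50% | 0.35 |
| 0.8 | 88.3% | 95.0% | 6.7 | 80% | 0.15 |
| 0.9 | 94.2% | 97.5% | 3.3 | 90% | 0.09 |
| 0.95 | 97.1% | 98.8% | 1.7 | 95% | 0.07 |

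With v₂ = 65% or 85% the share lost is identical. A 20/40 split gives window-only power of 0.72.

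**Event counts.** Assume 0.5 versus 1.0 vaccine-window AEs per patient, a Poisson model and 30 per batch, with z = difference / √(m₁/30 + m₂/30), where m₁ and m₂ are the mean counts per patient. The absolute difference stays at 0.5 throughout.

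| Other AEs per patient (assumed) | Ratio | z |
|---|---|---|
| 0 | 2.00 | 2.24 |
| 2 | 1.20 | 1.17 |
| 5 | 1.09 | 0.81 |
| 10 | 1.05 | 0.59 |
| 20 | 1.02 | 0.43 |

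**Does the relationship split solve it?** Only in part, on what the documents show. SAP 6.8 refers to treatment without naming a product, and Protocol 11.2 defines causality against the IMP, which may be Intuvax or sunitinib. Protocol 12.1.12 also tabulates by worst severity and worst relationship, so a later sunitinib event of higher grade or closer relationship could hide a vaccine reaction in the same patient. Attribution to Intuvax by name is required for dose-limiting toxicities (Protocol 11.5).

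**The case against.** The strongest defence is that the tables hold more than one any-AE row. SAP 6.3.10 describes the overview as also giving numbers of events and breakdowns by seriousness, intensity, action taken and relationship. A batch with more severe or more serious reactions could show in those rows. If relationship is recorded separately for each product, the relationship table answers much of the concern. Whole-study counting also has a purpose: Protocol 5.3 names a possible late immune reaction with organ damage, which a count stopped at nephrectomy would miss. Finally, the comparison is descriptive, and the AE listings give start day relative to first dose, so a windowed review by batch could be assembled. All of this stands. It limits the size of the problem and argues for keeping the whole-study split, but no windowed or acute batch display is actually planned.

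A reader might go further in three ways that the documents do not support.
- **That a batch difference is almost wholly lost.** This needs b of about 0.90 or more. A high background is plausible after surgery and sunitinib, but no rate is given, and the statement would concern the any-AE proportion, not event counts.
- **That pre-injection events are certainly in the batch tables.** The protocol wording points that way. The SAP wording is ambiguous: it has separate pre-treatment tables (14.3.1.10 and 14.3.1.11), a pre-treatment listing (16.2.7.4), and rules in SAP 6.6 that class AEs with incomplete dates as pre-treatment or treatment-emergent.
- **That batch is confounded with the change in sunitinib policy.** Before protocol version 4.0 the design did differ for one stratum: "Following this design intermediate risk subjects would only start sunitinib treatment after confirmed PD" (SAP 4.1). But nothing says when each batch was used, so use in sequence would be an assumption.

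**Conclusion.** The point holds as a matter of design. The only batch-split AE tables have no vaccine-related onset window, so they mix a window of 14 to 61 days with surgical and sunitinib events, and the 4-hour reaction table lacks a batch split. Dilution of the any-AE proportion equals b, which is unknown: 50% at b = 0.5 and 90% at b = 0.9, assuming independent and equal background risk in the two batches. Count differences keep their absolute size and lose ratio and precision. The supportable wording is that a batch difference may be substantially diluted. No primary or secondary efficacy result is affected; what improves is the interpretability of the sponsor's own batch question.

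**What to change.** - Split Table 14.3.1.9 by batch.
- Add to Tables 14.3.1.2 and 14.3.1.5 a version limited to AEs that start or worsen from the first Intuvax injection until nephrectomy, or until 30 days after the last Intuvax dose if there is no nephrectomy.
- State in SAP 6.8 that events before the first injection are excluded from the batch tables.
- If relationship is recorded per product, show relationship to Intuvax separately from relationship to sunitinib.
- Keep the whole-study batch split alongside, so that late immune events remain visible.

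A further split by stratum is optional: 60 patients over two batches and two strata is about 15 per cell if even.

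The cost is a few extra descriptive tables and an onset-date filter. No new data are needed for the windowed tables or the 4-hour split: AE start day is already listed (SAP 6.3.10) and the batch number is already documented (Protocol 9.7).

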6.9 Interim Analysis

An interim analysis is not planned for in this study.

6.10 Data Monitoring

Not applicable.

14.1 DEMOGRAPHIC DATA

(Baseline presentations will be based on the safety set overall and split by stratum if not otherwise stated below)

- 14.1.1 Patient Disposition in Analysis Sets and Reason for Exclusions (All included patients)
- 14.1.2 Patient Discontinuation (All included patients)
- 14.1.3 Number of Patients by Visit (Safety Set)
- 14.1.4 Demographics: Age, Sex and Race (Safety Set)
- 14.1.5 Number of Patients by Country (Safety Set)
- 14.1.6 Other Baseline Characteristics: Weight, Height (Safety Set)
- 14.1.7 Karnofsky Performance Status (Safety Set)
- 14.1.8 Medical History (mRCC): Duration of mRCC, TNM Stage, mRCC Symptoms and Severity Grade (Safety Set)
- 14.1.9 Medical and Surgical History (Excluding mRCC) (Safety Set)

14.2 EFFICACY DATA

(Efficacy presentations will be split by stratum, all presentation will be based on FAS if not otherwise stated below)

Tables

- 14.2.1 Life table statistics of OS by treatment group (FAS, PPS and Subgroups)
- 14.2.2 Quartile Estimates (Median) and Confidence Intervals for OS (FAS, PPS and Subgroups)
- 14.2.3 Log rank test compare survival functions for treatments groups OS (FAS, PPS and Subgroups)
- 14.2.4 The estimates of the second primary endpoint of the proportion of 18-months survival and corresponding z-test test. (FAS, PPS and Subgroup)

- 14.2.7 Life table statistics of PFS from start of Sunitinib by treatment group
- 14.2.8 Quartile Estimates (Median) and Confidence Intervals for PFS from start of Sunitinib (FAS and Subgroup)
- 14.2.9 Log-Rank test compare survival functions for treatment groups PFS from start of Sunitinib (FAS and Subgroup)
- 14.2.13 Summary of RECIST 1.1, Number of patients with CR, PR, PD, SD, and "Not Evaluable" by visit from Screening to Sunitinib Start Visit (FAS and Subgroup)
- 14.2.14 Summary of RECIST 1.1, Number of patients with CR, PR, PD, SD, and "Not Evaluable" by visit after Sunitinib Start Visit (FAS and Subgroup)
- 14.2.15 Summary of ORR and DCR from start of Sunitinib (FAS and Subgroup)
- 14.2.16 Cochran Mante -Haenze test for ORR and DCR (FAS and Subgroup)
- 14.2.17 Summary of duration of response, and duration of clinical benefit (FAS and Subgroup)
- 14.2.18 Summary of duration of stable disease (FAS and Subgroup)
- 14.2.19 Life table statistics of TTP from start of Sunitinib by treatment group (FAS and Subgroup)
- 14.2.20 Quartile Estimates (Median) and Confidence Intervals for TTP from start of Sunitinib (FAS and Subgroups)
- 14.2.21 Log-Rank test compare survival functions for treatment groups TTP from start of Sunitinib (FAS and Subgroups)
- 14.2.22 Summary of tumor infiltrating CD8+ T-cells and relative number of tumor infiltrating CD8+ T-cells, [REDACTED] and [REDACTED] (FAS and Subgroups)
- 14.2.23 Summary of ECOG performance by visit (FAS and Subgroups)
- 14.2.24 [REDACTED]
- 14.2.25 Summary of immunohistology parameters (CD8+ T-cells) in a biopsy from adjacent normal kidney tissue collected approximately 2 cm from the tumor margin and in a metastasis biopsy where applicable, [REDACTED] and [REDACTED] (FAS and Subgroups)
- 14.2.26 Summary of degree of MHC mismatch (HLA-A, HLA-B, and HLA-DRB1) between Intuvax (donor) and the patient (receiver) and intratumoral infiltration of CD8+ T-cells, [REDACTED] and [REDACTED] (FAS and Subgroups)
- 14.2.27 Summary table for auto- and allo-immunization parameters. (FAS and Subgroups)
- 14.2.28 Shift tables for auto- and allo-immunization parameters from prior to vaccination 1 to Sun-Start visit (FAS and Subgroups)
- 14.2.29 Life table statistics of TTF from Screening by treatment group (FAS and Subgroups)
- 14.2.30 Quartile Estimates (Median) and Confidence Intervals for TTF from Screening (FAS and Subgroups)
- 14.2.31 Log-Rank test compare survival functions for treatment groups TTF Screening (FAS and Subgroups)
- 14.2.32 Summary of CD8+tumor infiltration (FAS) by best overall response, ORR and DCR according to RECIST 1.1 during the trial (FAS and Subgroups)
- 14.2.33 [REDACTED]
- 14.2.34 [REDACTED]
- 14.2.35 [REDACTED]
- 14.2.36 [REDACTED]
- 14.2.37 Summary of Sunitinib dose density (FAS) by ORR, DCR and best overall response according to RECIST 1.1 during the trial (FAS and Subgroups)

14.2.38

14.2.39

Figures

- 14.2.35 Kaplan-Meier plots OS survival functions by treatment group (FAS, PPS, Subgroups)
- 14.2.36 Kaplan-Meier plots PFS survival functions by treatment group (FAS, PPS, Subgroups)
- 14.2.37 Kaplan-Meier plots TTP survival functions by treatment group (FAS, Subgroups)
- 14.2.38 Kaplan-Meier plots TTF survival functions by treatment group (FAS, Subgroups)
- 14.2.39 Waterfall charts over the response distribution (FAS and Subgroups)
- 14.2.40 Swimmer plots time from screening (FAS and Subgroups)
- 14.2.41 Swimmer plots time from randomization (FAS and Subgroups)
- 14.2.42 Plot over mismatch patient/donor and CD8+ T-cells (as analysed by [REDACTED]) and corresponding Spearman correlation (FAS and Subgroups)
- 14.2.43 Plot over mismatch patient/donor and CD8+ T-cells (as analysed by [REDACTED]) and corresponding Spearman correlation (FAS and Subgroups)

14.3 SAFETY DATA

(Safety presentations will be based on the safety set unless otherwise stated below)

14.3.1 Displays of Adverse Events

- 14.3.1.1 Summary of Adverse Events
- 14.3.1.2 Summary of Adverse Events by ilixadencel batch subgroup
- 14.3.1.3 Adverse Events by System Organ Class and Preferred term
- 14.3.1.4 Adverse Events: Number of Patients by Intensity and Relationship by Treatment
- 14.3.1.5 Adverse Events: Number of Patients by Intensity and Relationship by Treatment by ilixadencel batch subgroup
- 14.3.1.6 Serious Adverse Events by System Organ Class and Preferred term
- 14.3.1.7 Related Adverse Events by System Organ Class and Preferred term
- 14.3.1.8 Adverse Events by CTCAE grade and System Organ Class and Preferred term
- 14.3.1.9 Adverse Events occurring 4 hours following the Intuvax vaccination
- 14.3.1.10 Adverse Events occurring between first assessment at Screening and first Intuvax dose
- 14.3.1.11 Adverse Events occurring between first assessment at Screening and Nephrectomy
- 14.2.1.12 Related Serious Adverse Events by System Organ Class and Preferred term

14.3.2 Listings of Deaths, Other Serious Adverse Events, and Other Significant Adverse Events

- 14.3.2.1 Listings of Deaths, Other Serious Adverse Events, and Other Significant Adverse Events

14.3.4 Abnormal Laboratory Value Listings

- 14.3.4.1 Abnormal Laboratory Value Listing
- 14.3.4.2 Other Relevant Laboratory Analyses

14.3.4.3 Summary Statistics by Visit/Timepoint with Difference from Baseline (including the number of abnormal (low and high) and clinically significant observations)

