Minimal, local or noninvasive intervention indicated OR limiting age-appropriate instrumental Activities of Daily Living (ADL). (Instrumental ADL refer to preparing meals, shopping for groceries or clothes, using the telephone, managing money, etc.)

Grade 3 (Severe or medically significant but not immediately life-threatening)

Hospitalization or prolongation of hospitalization indicated OR disabling OR limiting self-care ADL. (Self-care ADL refer to bathing, dressing and undressing, feeding self, using the toilet, taking medications, and not bedridden.)

Grade 4 (Life-threatening consequences)

Urgent intervention indicated.

Grade 5 (Death related to AE)

If an AE changes in severity, the worst severity should be reported.

Causality

Causality will be assessed as:

Probable

A clinical event, including laboratory test abnormality, with a reasonable time sequence to administration of the IMP, unlikely to be attributed to concurrent disease or other drugs or chemicals, and which follows a clinically reasonable response on withdrawal (dechallenge). Rechallenge information is not required to fulfil this definition.

Possible

A clinical event, including laboratory test abnormality, with a reasonable time sequence to administration of the IMP, but which could also be explained by concurrent disease or other drugs or chemicals. Information on IMP withdrawal may be lacking or unclear.

Unlikely

A clinical event, including laboratory test abnormality, with a temporal relationship to IMP administration which makes a causal relationship improbable, and in which other drugs, chemicals or underlying disease provide plausible explanations.

Follow-up of Patients after Adverse Events

Any AE that is ongoing when the patient is withdrawn from the study should be followed up until the AE is resolved or the Investigator decides that the AE is stable and needs no further follow-up.

Abnormal Laboratory Values/Vital Signs

The reporting of abnormalities as both laboratory/vital signs findings and AEs should be avoided.

An asymptomatic abnormal laboratory/vital sign finding should only be reported as an AE if it is clinically significant, if it fulfils the criteria for an SAE or if it causes the patient to discontinue the study.

If an abnormal laboratory/vital sign value is associated with clinical signs and symptoms, the sign/symptom should be reported as an AE and the associated laboratory/vital sign result should be considered additional information.

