12.1.13 Other Safety Assessments

Physical Examination

Physical examination data will be summarized by visit and treatment group as described in *Section 12.1.4*.

Vital Signs

Vital signs will be summarized by visit and treatment group, together with changes from Screening as described in *Section 12.1.4*.

Vital signs assessed during vaccination, will be summarized both by nominal time point and as change from the pre-vaccination at each post-vaccination time point.

Laboratory Safety Assessments

For laboratory data, summary statistics will be produced for observed values and for changes from screening to each visit as described in *Section 12.1.4*. In addition, the number of abnormal and clinically significant observations will be tabulated for each treatment group by visit. Abnormal values will be flagged in listings.

Shift tables will show the number of patients who changed from below, within or above the reference range at Screening to below, within or above the reference range at each time of assessment.

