4 OVERALL STUDY DESIGN

4.1 Overview of Study Design

The study is an open-label, randomized, controlled, two (2) armed, multicenter, phase II study. Intermediate- and high-risk mRCC patients according to Heng criteria are eligible for participation. Patients are stratified and randomised based on Heng-risk.

High-risk mRCC patients are included according to the following criteria:

Patients fulfilling three (3) to six (6) of the following prognostic factors:

- Hemoglobin (Hb) less than the lower limit of normal (LLN)
- Corrected Calcium (Ca) greater than upper limit of normal (ULN)
- Karnofsky performance status less than 80%
- Time for diagnosis to treatment less than one (1) year
- Neutrophils greater than ULN
- Platelets greater than ULN

Intermediate-risk mRCC patient according to criteria

One (1) or two (2) of the following prognostic factors:

- Hb less than the lower limit of normal (LLN)
- Corrected Ca greater than upper limit of normal (ULN)
- Karnofsky performance status less than 80%

- Time for diagnosis to treatment less than one (1) year
- Neutrophils greater than ULN
- Platelets greater than ULN

The patients are randomized in a consecutive order to one (1) of the following two (2) treatment arms when eligibility has been confirmed;

- (i) Two (2) doses of Intuvax (10x10⁶ DCs) administered intratumorally into the primary tumor 14 ±3 days apart followed by nephrectomy at least three (3) days after the second vaccine dose and sunitinib treatment initiated five (5) to eight (8) weeks after nephrectomy, administered dose in accordance with the SmPC/USPI.
- (ii) Sunitinib treatment initiated five (5) to eight (8) weeks after nephrectomy, administered dose in accordance with the SmPC/USPI.

The expected number of patients to be randomized in the study is around 90. The patients are randomized in a 2:1 (vaccine treatment arm [i]:control treatment arm [ii]) ratio.

Patients randomized to treatment arm (i) are scheduled for 12 study visits and patients randomized to treatment arm (ii) are scheduled for 10 study visits during a study period of 78 weeks, see list below and Figure 1. The following visits apply for patients participating in the trial

- Screening Visit (Screening)
- Vaccination 1 Visit (Vacc1), applicable for patients randomized to treatment arm (i)
- Vaccination 2 Visit (Vacc2), applicable for patients randomized to treatment arm (i)
- Nephrectomy Visit (Nephrectomy)

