6.3.11 Other Safety Assessments

Vital Signs

For vital signs parameters (systolic and diastolic blood pressure, supine heart rate and temperature) summary statistics will be produced for observed values by visit. In addition, the difference from baseline to each visit at which they were assessed will be derived and presented.

Vital signs assessed at time points post vaccination will be summarised separately.

Clinical Laboratory Measurements

The laboratory categories are Hematology, Clinical Chemistry, Coagulation, Urine analysis and Pregnancy analysis.

For all laboratory parameters, summary statistics will be produced for observed values by visit. In addition, the difference from baseline to each visit at which they were assessed will be derived and presented. The number of abnormal (low and high) and clinically significant observations will be tabulated for each treatment group by visit. Abnormal values will be flagged in listings.

Shift tables that show the number of patients who changed from low, normal or high at baseline to low, normal or high at each post-baseline time of assessment will be presented.

Physical Examination

Physical examination results will be tabulated including number of subjects with normal, abnormal not clinically significant or clinically significant abnormalities by visit. Corresponding shift tables for changes from baseline will be presented, and all the results will be listed.

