14.3.4.4 Shift Tables

14.3.5 Extent of Exposure

14.3.5.1 Exposure vaccination

14.3.5.2 Exposure sunitinib and sunitinib dose density

14.3.6 Vital Signs

14.3.6.1 Summary Statistics with Difference from Baseline for Vital Signs (Systolic Blood Pressure, Diastolic Blood Pressure, Heart Rate and weight)

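### Laboratory shift tables use three reference-range classes and no severity-graded laboratory table is planned, so further worsening in patients who enter out of range shows no shift

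*SAP*

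**What the plan says.** The categories are set in the text, not in the table list. SAP 6.3.11 plans shift tables of patients "who changed from low, normal or high at baseline to low, normal or high at each post-baseline time of assessment". Protocol 12.1.13 plans the same thing: "below, within or above the reference range at Screening to below, within or above the reference range at each time of assessment". SAP Appendix 1 carries this as "14.3.4.4 Shift Tables" without further detail.

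The other planned laboratory displays are:
- Table 14.3.4.3, "Summary Statistics by Visit/Timepoint with Difference from Baseline (including the number of abnormal (low and high) and clinically significant observations";
- observed values and change from baseline by visit, with mean, SD, quartiles, minimum and maximum, by arm and stratum (SAP 6.3.2 and 6.3.11);
- abnormal-value and individual listings (14.3.4.1 and 16.2.8.1).

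CTCAE v4.0 grades are used for adverse events (Protocol 11.2; SAP Table 14.3.1.8) but for no laboratory table.

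On who enters, Protocol 8.2 accepts hemoglobin from 90 g/L, creatinine and bilirubin up to 1.5 × ULN, and ALAT/ASAT up to 2.5 × ULN, with a limit of 5 for liver metastases. Calcium has no entry limit. SAP 4.1 defines the high-risk stratum as "Patients fulfilling three (3) to six (6) of the following prognostic factors". Four of those six factors are out-of-range laboratory values: hemoglobin below LLN, and corrected calcium, neutrophils or platelets above ULN.

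**The concern.** A three-class shift table works when most patients start within range. Here the entry rules and the stratification factors bring in patients who start outside it. If hemoglobin is already low, or a liver test already high, no further deterioration can move the patient to another cell. Among patients who start normal, a value just past the limit and a value many times the limit fall in the same cell.

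Safety and tolerability is a secondary objective, and laboratory assessments are a named safety endpoint (SAP 3.4). Creatinine is a foreseeable case: Protocol 5.1 reports that renal function fell after nephrectomy in all patients of the earlier study, and both arms here have nephrectomy.

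**Working it through.** The plan gives no figure to reproduce. Two logical checks apply.

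**1. Does worsening register?** Take a patient at the entry limit (Protocol 8.2), multiply the value by an illustrative factor, and classify it as high if it exceeds 1 × ULN. The factors are assumptions.

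| Parameter | Baseline (× ULN) | × 1.01 | × 2 | × 5 | × 10 | Shift cell |
|---|---|---|---|---|---|---|
| Creatinine, bilirubin | 1.5 | 1.515 | 3 | 7.5 | 15 | high to high, all four |
| ALAT, ASAT | 2.5 | 2.525 | 5 | 12.5 | 25 | high to high, all four |

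A 1% rise and a ten-fold rise cannot be told apart. The same holds for hemoglobin falling from below LLN and calcium rising from above ULN.

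**2. How common is an out-of-range baseline?** Entry requires diagnosis less than 6 months earlier (about 184 days, taken here as counted to Screening). The latest scheduled sunitinib start is 63 days to nephrectomy plus 8 × 7 = 56 days, so 63 + 56 = 119 days after Screening. From diagnosis that is at most about 184 + 119 = 303 days, under one year. The Heng factor on time from diagnosis to treatment is therefore met by every patient treated on schedule.

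- High risk needs at least 3 of 6 factors, so at least 3 − 1 = 2 of the remaining 5. Only Karnofsky status is not a laboratory value, so at least 2 − 1 = 1 laboratory factor is out of range, and at most 4.
- In France, Karnofsky 70% or less is excluded, so the Karnofsky factor (below 80%, on a scale in steps of 10) cannot be met. The range becomes 2 to 4.
- Intermediate risk (1 or 2 factors in total) gives 0 or 1.

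**3. Which of these are blind spots?** The loss is directional. Platelets or neutrophils above ULN that fall to normal or low do change cell, and entry requires platelets of at least 150 and leukocytes of at least 4.5 × 10^9/L, which limits low starting counts. A patient can be high-risk through neutrophils and platelets alone (1 + 2 = 3 factors) and have no blind spot for a fall in either. Check 2 therefore shows that out-of-range baselines are built into the high-risk stratum. It does not count the patients whose worsening would be hidden.

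**The case against.** The strongest reply is that severity appears elsewhere. Table 14.3.4.3 counts clinically significant values by arm and visit. Change from baseline comes with minimum and maximum, so an ALAT of 25 × ULN would tend to set the maximum for its arm, stratum and visit. With about 90 patients, the listings can be read. Laboratory findings that become adverse events are graded and tabulated, and Protocol 11.2 asks sites to report laboratory findings even when they may reflect progression. Protocol and SAP agree with each other, the trial is exploratory, no decision rule rests on these tables, and the undefined Table 14.3.4.2 (other laboratory analyses) could hold a graded display.

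Much of this stands. A reader might infer that low/normal/high is the only laboratory display, or that severity is lost altogether in patients who start out of range. The documents support neither reading: the loss is in the shift tables, and the other displays recover part of it.

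They recover only part, for these reasons:
- The clinical-significance flag is an ungraded site judgement in an open-label trial.
- Means, quartiles and extremes by visit do not say how many patients worsened, how far, or from what baseline.
- The adverse-event route is conditional: "An asymptomatic abnormal laboratory/vital sign finding should only be reported as an AE if it is clinically significant", or if it meets seriousness criteria or causes discontinuation. Where symptoms are present, the symptom is the event and the laboratory value is supporting information. The instruction on progression concerns how to report events without using that general term, and does not remove these conditions.
- Under SAP 6.6, unscheduled values enter by-visit displays only where the scheduled value is missing. Extra Visits are held for symptoms and include blood tests (Protocol 7.2.1.9), so an extreme value there can be absent even from the maximum.
- Listings are not an arm comparison, and nothing commits Table 14.3.4.2 to a graded one.

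**Conclusion.** The point holds as a limit on how sensitively laboratory safety is reported. The shift tables have three classes per visit, no severity-graded or worst-post-baseline laboratory table is planned, and same-direction worsening from an out-of-range baseline shows no shift whatever its size.

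Its extent in patients is unknown. Every high-risk patient treated on schedule has at least one Heng laboratory factor out of range, and a reader might infer that all high-risk patients are affected or that marrow toxicity in them is hidden. That does not follow, because a fall in neutrophils or platelets from above ULN does register, although every depth of low shares one cell. The documents give no baseline frequencies for low hemoglobin, high calcium, raised liver tests or raised creatinine, and the entry limits are ceilings, not prevalences.

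The conclusion rests on the printed text of SAP 6.3.11 and Appendix 1. The primary analysis and the sample size are not affected. It is worth changing because the safety objective is explicit, the protocol already uses CTCAE v4.0, and the cost is low.

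**What to change.** In SAP 6.3.11 and Table 14.3.4.4, add a shift table from baseline CTCAE v4.0 grade to worst post-baseline grade for every gradable parameter. Present it by arm and stratum, keep low and high directions separate, and include unscheduled values in the worst grade. Report the number of patients reaching grade 3 or higher in each arm. Keep low/normal/high for parameters without a grade. If the reference-range tables are dropped for graded parameters, record that in SAP 6.1, since Protocol 12.1.13 plans them.

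The cost is SAP wording and programming. The values are recorded, and the planned shift tables already need the reference ranges. One convention must be written down: CTCAE terms with a clinical component are graded on the numeric criterion alone. No visit, assessment or analysis set changes.
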